2.2. Endpoints

2.2.1 Stage 1

2.2.1.1 Primary:

Pharmacokinetic profile (including C_{max}, Cl and AUC) of micronised progesterone after single doses of 200mg and 600mg in >4 of 6 patients that allow estimation of serum progesterone exposure (AUC) that is 50 – 150% of that targeted in order to determine the dose in Stage 2..

2.2.2 Stage 2

2.2.2.1 Primary:

- ≥ 13 of 18 patients able to tolerate micronised progesterone until the end of the 14-day treatment period at a dose predicted to achieve the target progesterone exposure.
- Trough progesterone concentrations within 50 – 150% of target

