9.2.2 Stage 2 recruitment is less than anticipated

We have looked at the number of potentially eligible patients and our recruitment plan is conservative. In the event of recruitment slowing we will engage with colleagues, in particular those in the lung cancer and melanoma team; [name] is a senior member of the breast team. In the event of a further “surge” in COVID-19 cases, mandating suspension of recruitment and redeployment of trial staff, we will record all such instances and seek recompense from the NHS or other bodies for whom they are temporarily working. Patients discontinuing for reasons other than progesterone toxicity will be replaced.

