10. WITHDRAWAL OF SUBJECTS

Patients may withdraw from the study at any point, including after giving consent to the trial but before starting treatment; no further data collection will take place.

Patients may discontinue the study for reasons including toxicity, non-compliance, withdrawal of consent or if the investigator judges' continuation not to be in the patient's best interest. Any patient who does not start IMP, will be replaced.

In Stage 1, patients from whom two full pharmacokinetic profiles cannot be obtained will also be replaced

In Stage 2, patients withdrawing due to the toxicity of micronised progesterone will be replaced. The patients replaced will, however, remain evaluable for assessment of tolerability and if such withdrawals occur in >20% of patients the combination of progesterone and dexamethasone will be considered unacceptably toxic.

If at any point throughout the trial, a patient becomes unable to swallow, they should be withdrawn.

Any patients who permanently discontinue IMP should receive the non IMP dexamethasone and other standard of care treatments.

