11.3 Micronised progesterone/placebo (IMP)

Micronised progesterone/placebo is the trial IMP and will be provided by the manufacturer as 200mg capsules. Progesterone/placebo should be taken orally within 30 minutes of finishing a meal.

Stage 1: Day 1-10 (Please refer to Appendix No.6 - Doses Stage 1)

On Day 1, patients will take 200mg micronized progesterone in the morning after breakfast (08.00 - 10.00).

A further dose of 600mg of micronized progesterone will be taken on another day between Days 5-10. This day will be decided by the clinical team and patient.

Stage 2: Day 1-22 (Please refer to Appendix No.7 - Doses Stage 2)

The Stage 2, Day 1 starting dose of micronized progesterone/placebo will be determined by the pharmacokinetic results of Stage 1.

In Stage 2, patients will also take progesterone/placebo at 08.00 - 10.00 (breakfast), 12.00 – 14.00 (lunch) and 17.00 – 19.00 (dinner). Patients will record the time each meal is completed and micronised progesterone (or placebo in Stage 2) taken.

Patients will continue on this dose to Day 14 unless they do not tolerate this initial micronised progesterone/placebo dose due to side-effects. In that case, the dose of micronized progesterone/placebo will be reduced by 200mg; if that reduced dose is not tolerated, it will be reduced by a further 200mg. If the second reduced dose is not tolerable, the patient will be withdrawn from the study. For example, if the initial dose of micronized progesterone/placebo was 600mg t.d.s (three times a day) i.e. 1800 mg/day, the first dose reduction would be 400mg t.d.s, i.e. 1200mg/day in total and further dose reduction would be 200mg t.d.s. i.e. 600mg/day in total.

See Appendix 6 [Drug Table Stage 1] and Appendix 7 [Drug Table Stage 2]) for Drug tables.

Day 15-22 involves trials procedures but not micronized progesterone/placebo.

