15.5 Analysis Plan

The final analysis will be performed on the evaluable population (that is, patients who successfully completed the 14-day treatment period and were not subsequently found to be ineligible); no interim analysis is planned. Unless otherwise stated, 80% confidence intervals will be used; 1-sided p-values calculated and $\alpha=0.05$ as a threshold for significance. Substantial missing data (i.e., missing in >10% patients) will be highlighted in statistical study reports but not imputed. A full statistical analysis plan will be developed prior to any analyses being performed.

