14.4 Final analysis

The final analyses will be performed once the end of study has been declared. They will address each endpoint explicitly with evidence, including:

- Stage 1, primary endpoint (Section 2.2.1.1 Primary:) – to be assessed at end of Stage 1
 - Percentage of target exposure for each patient will be calculated and presented. Subsequent counts of number of patients to achieve 50-150% of target exposure will be presented.
- Stage 2, primary endpoint (Section 2.2.2.1 Primary:) – to be assessed at end of Stage 2
 - Number of patients tolerating progesterone until the end of the 14-day treatment period will be calculated and presented. Note that at least 13/18 patients should

be identified as tolerating progesterone (i.e., ensuring that >50% patients, using 80% CI, tolerate the treatment).

- Stage 2, secondary endpoint (Section 2.2.2.2 Secondary) – to be assessed at end of Stage 2
 - Compliance data will be presented and the number of patients complying with protocol guidelines on dose reduction will be calculated and presented. Note that at least 13/18 patients should be identified as complying with the dose reduction guidelines, to demonstrate compliance (i.e., ensuring that >50% patients, using 80% CI, comply).
 - Dexamethasone related side-effects will be coded according to the CTCAE toxicity criteria. These data will be presented in several ways, including worst value over the trial period for each patient and tabulation of all side-effects graded \geq grade 1 in at least 10% of patients.
 - Presentation/analysis of QoL (DSQ-C, EORTC QLQ-30 & BN20) data.
 - Calculation of percentage reduction in dexamethasone at Day 14.
 - Comparison of final dexamethasone dose in the progesterone and placebo arms (e.g., by ordered logistic regression).
 - Comparison of cumulative dexamethasone dose in the progesterone and placebo arms (e.g. by ANOVA/t-test or Mann Whitney U if normality assumptions are violated).
 - Comparison of time to reach final dose in each arm in the progesterone and placebo arms (e.g., Cox regression).
- Stage 2, tertiary endpoint (Section 2.2.2.3 Tertiary) – to be assessed at end of Stage 2
 - Presentation of relevant lab results to assess endocrine, liver function and lipid profiles in patients on progesterone.
 - Comparison (progesterone v placebo) of CT/MRI data (including tumour size, enhancement pattern etc)

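### The Stage 2 tolerability count is restricted to 14-day completers, so its completion part is met by construction, and Section 10 contradicts this without fixing the denominator

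*Protocol*

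**What the plan says.** Section 2.2.2.1 sets the Stage 2 primary endpoint as at least "13 of 18 patients able to tolerate micronised progesterone until the end of the 14-day treatment period", with the further condition "at a dose predicted to achieve the target progesterone exposure".

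Section 15.5 defines the evaluable population for the final analysis as "patients who successfully completed the 14-day treatment period and were not subsequently found to be ineligible". Section 14.4 (Final analysis) lists the primary count within that analysis: "Number of patients tolerating progesterone until the end of the 14-day treatment period will be calculated and presented". It explains 13/18 as showing, with an 80% confidence interval, that more than half of patients tolerate treatment. It names no other population and does not repeat the dose condition.

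On replacement:
- Section 3.1.6 recruits 36 evaluable patients and replaces those who are not evaluable.
- Section 9.2.2 adds: "Patients discontinuing for reasons other than progesterone toxicity will be replaced".
- Sections 9.2.3 and 10 also replace patients who withdraw for progesterone toxicity. Both call the combination unacceptably toxic if such withdrawals exceed 20%, and 9.2.3 makes this an exception to replacement.
- Section 10 says of the replaced toxicity withdrawals: "The patients replaced will, however, remain evaluable for assessment of tolerability".

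Section 11.3 allows two dose reductions before withdrawal: the dose "will be reduced by 200mg; if that reduced dose is not tolerated, it will be reduced by a further 200mg". A patient can therefore complete 14 days on a reduced dose.

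**The concern.** Staying on progesterone to Day 14 is the event that the endpoint measures, and under Section 15.5 it is also the condition for entering the analysis. With replacement up to 18 evaluable patients per arm, the completion part is satisfied before any data are seen.

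Section 10 points the other way for toxicity withdrawals, so the protocol uses the word evaluable in two incompatible senses for one primary endpoint, and nothing says which governs. Patients who stop for non-compliance or withdrawn consent are not brought back under either rule, although acceptability belongs to the primary aim in Section 2.1.1.

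Section 15.3 calls safety the primary outcome, and Section 9.1 makes confirmed tolerability one of the grounds for a Phase 3 trial. The choice of population can decide that result.

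**Working it through.** **Inputs.** Criterion 13 of 18 (2.2.2.1, 14.4); 80% confidence interval (15.5, 14.4); 18 patients per arm (15.4); replacement and the 20% limit (3.1.6, 9.2.2, 9.2.3, 10). The protocol gives no expected tolerability rate, so a range is assumed.

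**1. Reproducing 13/18.** The exact (Clopper-Pearson) two-sided 80% lower limit for x of n is the 0.10 quantile of Beta(x, n − x + 1).
- 13/18 = 72.2%: lower limit 54.5%, above 50%.
- 12/18 = 66.7%: lower limit 48.8%, below 50%.

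So 13 is the exact minimum for n = 18. Wilson, Wald, Agresti-Coull and Jeffreys intervals would already accept 12 (lower limits 51.5% to 52.4%). The protocol names no interval method; the exact one is the one that gives 13.

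**2. The rule on 18 treated patients, against completers.** For 18 patients starting progesterone with none replaced in the count, P(pass) = P(X ≥ 13), X ~ Binomial(18, p). For completers with full replacement, the completion part passes with probability 1 at every p, and 18/p patients are expected to start progesterone.

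| Assumed true tolerability p | P(≥13 of 18 treated) | Completion part among completers | Expected starters, 18/p |
|---|---|---|---|
| 0.4 | 0.006 | 1 | 45 |
| 0.5 | 0.048 | 1 | 36 |
| 0.6 | 0.209 | 1 | 30 |
| 0.7 | 0.534 | 1 | 25.7 |
| 0.8 | 0.867 | 1 | 22.5 |
| 0.9 | 0.994 | 1 | 20 |

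The last two columns ignore the 20% limit, which could end replacement earlier.

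**3. Adding back the withdrawals that Section 10 retains.** With 18 completers and k retained withdrawals the result is 18/(18 + k). Since 18 ≥ 13 for every k, a fixed count of 13 is always reached. Read as a proportion or a confidence limit, the criterion can fail:
- k = 5: 18/23 = 78.3%, lower limit 63.4%; withdrawals 5/23 = 21.7%, above 20%.
- k = 7: 18/25 = 72.0%, just below 13/18 = 72.2%.
- k = 10: 18/28, lower limit 50.4%.
- k = 11: 18/29, lower limit 48.5%, below 50%.

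**4. The count that matches each denominator.** The smallest x with an exact lower limit above 50% is 13 for n = 18 or 19, 14 for 20 or 21, 15 for 22 and 16 for 23. A count of 13 does not carry over: the limit for 13/20 is 48.2% and for 13/23 is 41.1%.

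**5. The 20% limit against 13/18.** Taking the 18 treated progesterone patients as denominator: 4/18 = 22.2% leaves 14 tolerating, and 5/18 = 27.8% leaves 13. Both satisfy the endpoint and both exceed 20%.

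**The case against.** The best defence is that Section 10 is the specific rule for tolerability and should override the general population in 15.5. Replaced toxicity withdrawals then count, and more than 20% of them condemns the combination whatever the 13/18 count shows. In an 18-completer arm that happens at the fifth such withdrawal. A full analysis plan is also promised before any analysis, and Section 2.2.2.1 has a second primary endpoint, trough concentration, that checks exposure separately.

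Much of this stands. A reader might infer that the criterion can never fail, that every drop-out is replaced, or that the endpoint says nothing about tolerability. The documents do not support these readings. Section 10 retains toxicity withdrawals, 9.2.3 stops replacement above 20%, and the dose condition in 2.2.2.1 could fail some completers whose dose was reduced.

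Two numerical inferences should also be avoided. Replacement up to 18 completers leads to 18/20 or 18/23 (lower limits 75.5% and 63.4%), not to 13/20 or 13/23; the latter only show that 13 is tied to its denominator. Nor can one say that a patient reduced from 600 to 200 mg falls below the 50% exposure floor. That floor is a share of target exposure, one third of the starting exposure is a different quantity, the 600 mg start is only an example, and the Stage 2 dose is not yet set.

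The defence does not remove the defect. Section 15.5 fixes the population itself, so an analysis plan could repair this only by departing from it. The 20% limit is not part of the endpoint in 2.2.2.1 or 14.4. Section 10 says nothing of patients who stop for other reasons.

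**Conclusion.** The point holds as a contradiction and an undefined denominator in the primary endpoint. Under 15.5 and 14.4 as written, with replacement, the completion part of 13/18 is met with probability 1; the same count applied to 18 treated patients would be met 4.8% of the time at 50% true tolerability and 53.4% at 70%. Under Section 10, a fixed count of 13 is still always reached by 18 completers. The 20% limit mitigates this but conflicts with the endpoint at 4 or 5 withdrawals among 18.

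This rests on three assumptions: replacement runs until 18 progesterone patients complete, the interval is the exact one that reproduces 13, and the 20% limit is taken over the progesterone arm (the protocol does not state its denominator). It should be corrected before unblinding, because the choice of population could otherwise be made with the result in view.

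**What to change.** - **Section 15.5:** name a tolerability and safety set of all Stage 2 patients who took at least one dose of IMP, by arm, including those later replaced. Limit the completer population to other analyses.
- **Sections 2.2.2.1 and 14.4 (Final analysis):** replace the fixed count by the rule that the exact 80% lower confidence limit exceeds 50%, with examples 13/18, 14/20, 15/22 and 16/23.
- **Who counts:** score toxicity withdrawals as failures. Report non-toxicity discontinuations separately by reason, with a sensitivity analysis that scores them as failures. This keeps events such as pregnancy or a newly needed excluded medicine from being labelled intolerance in the main count.
- **Dose condition:** carry the target-exposure condition of 2.2.2.1 into the 14.4 count and list patients who finish on a reduced dose separately.
- **Reconcile** 2.2.2.1, 9.2.3, 10, 11.3, 14.4 and 15.5, including the 20% limit against 13/18 and the denominator of each. Which toxicity limit is right is a clinical decision and is not proposed here.

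The cost is protocol and analysis-plan wording, with no extra patients. The reported tolerability may be less favourable than a completer count would show.

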14.4 Final analysis

The final analyses will be performed once the end of study has been declared. They will address each endpoint explicitly with evidence, including:

- Stage 1, primary endpoint (Section 2.2.1.1 Primary:) – to be assessed at end of Stage 1
 - Percentage of target exposure for each patient will be calculated and presented. Subsequent counts of number of patients to achieve 50-150% of target exposure will be presented.
- Stage 2, primary endpoint (Section 2.2.2.1 Primary:) – to be assessed at end of Stage 2
 - Number of patients tolerating progesterone until the end of the 14-day treatment period will be calculated and presented. Note that at least 13/18 patients should

be identified as tolerating progesterone (i.e., ensuring that >50% patients, using 80% CI, tolerate the treatment).

- Stage 2, secondary endpoint (Section 2.2.2.2 Secondary) – to be assessed at end of Stage 2
 - Compliance data will be presented and the number of patients complying with protocol guidelines on dose reduction will be calculated and presented. Note that at least 13/18 patients should be identified as complying with the dose reduction guidelines, to demonstrate compliance (i.e., ensuring that >50% patients, using 80% CI, comply).
 - Dexamethasone related side-effects will be coded according to the CTCAE toxicity criteria. These data will be presented in several ways, including worst value over the trial period for each patient and tabulation of all side-effects graded \geq grade 1 in at least 10% of patients.
 - Presentation/analysis of QoL (DSQ-C, EORTC QLQ-30 & BN20) data.
 - Calculation of percentage reduction in dexamethasone at Day 14.
 - Comparison of final dexamethasone dose in the progesterone and placebo arms (e.g., by ordered logistic regression).
 - Comparison of cumulative dexamethasone dose in the progesterone and placebo arms (e.g. by ANOVA/t-test or Mann Whitney U if normality assumptions are violated).
 - Comparison of time to reach final dose in each arm in the progesterone and placebo arms (e.g., Cox regression).
- Stage 2, tertiary endpoint (Section 2.2.2.3 Tertiary) – to be assessed at end of Stage 2
 - Presentation of relevant lab results to assess endocrine, liver function and lipid profiles in patients on progesterone.
 - Comparison (progesterone v placebo) of CT/MRI data (including tumour size, enhancement pattern etc)

Acceptability of (future) trial design, randomisation, and outcome measures including PROMs. Any deviations from the original statistical plan will be discussed with the DMC and fully described and justified in statistical study reports.

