1.5.4 Micronised progesterone for administration (Utrogestran)

Details of micronised progesterone are contained in the current version of the SmPC. Of note, much of the information in the SmPC relates to the approved use of micronised progesterone in combination with oestrogen in post-menopausal women with an intact uterus at potential risk of endometrial cancer, as hormone replacement therapy.

Micronised progesterone is not taken with food in routine practice as this increases its bioavailability. The recommended daily dose is 100 mg or 200 mg daily at bedtime.

With regard to potential drug interactions, drugs known to induce hepatic CYP450-3A4 such as anti-epileptic agents (phenytoin, carbamazepine) may increase the metabolism and elimination of progesterone; ketokonazole and other inhibitors of CYP450-3A4 may increase the bioavailability of progesterone.

The incidence of adverse drug reactions with oral micronised progesterone was calculated as 1.43/1,000 patient years', corresponding to approximately 1.5 spontaneously reported cases in every 1000 patients exposed. Clinical trial data comparing micronised progesterone in combination with conjugated oestrogen to conjugated oestrogens alone or placebo suggest an excess of headache and breast tenderness in those taking micronised progesterone. Somnolence, fatigue or transient dizziness may occur 1 to 3 hours after intake of micronised progesterone and is reported to be associated with high doses of progesterone. Withdrawal vaginal bleeding may occur in women in the week following discontinuation.

Micronised progesterone is absorbed by the digestive tract and in healthy volunteers plasma progesterone levels were maximum 2.2 +/- 1.4 hours following administration. Progesterone is highly (96%-99%) protein bound, primarily to serum albumin and transcortin. Progesterone is metabolised primarily by the liver predominantly 20 α hydroxy- Δ 4 α - prenone and 5 α - dihydroprogesterone. The elimination half-life observed is 16.8 +/- 2.3 hours with urinary elimination accounting for 95% in the form of glycoconjugated metabolites. The pharmacokinetics of micronized progesterone are reported as independent of dose. Individual pharmacokinetic characteristics were maintained over several months.

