9. SUCCESS CRITERIA AND BARRIERS TO PROPOSED WORK

9.1 Success criteria

The PROSSPER trial will have been successful if it generates results that underpin a subsequent definitive Phase 3 efficacy trial by

- Defining the oral dose of micronised progesterone required to reach target serum levels
- Confirming the acceptability, tolerability and safety of micronised progesterone, at the selected dose, in this patient population
- Verifying the acceptability and utility of the dexamethasone dose reduction protocol
- Collecting QoL data and PROMs relevant to the symptoms of raised intracranial pressure and dexamethasone side effects
- Demonstrating possible efficacy of micronised progesterone in reducing the dose of dexamethasone needed to control symptoms of cerebral oedema
- Establishing that a Phase 3 trial would be feasible and acceptable to patients.

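### The Stage 2 tolerability count in Section 14.4 omits the dose condition of the primary endpoint in Section 2.2.2.1, so dose-reduced completers can reverse the 13/18 verdict

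*Protocol*

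**What the plan says.** All references are to the protocol.

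- **Endpoint (2.2.2.1).** At least 13 of 18 patients must tolerate progesterone "until the end of the 14-day treatment period at a dose predicted to achieve the target progesterone exposure". A second primary endpoint, trough concentrations within 50–150% of target, is listed with no required number of patients.
- **Aim and success criterion (2.1.1, 9.1).** The primary aim concerns a dose that reaches the target exposure. Section 9.1 lists "Confirming the acceptability, tolerability and safety of micronised progesterone, at the selected dose".
- **Count (14.4, Final analysis).** "Number of patients tolerating progesterone until the end of the 14-day treatment period will be calculated and presented". The threshold is again 13/18, explained as "ensuring that >50% patients, using 80% CI, tolerate the treatment". No dose is mentioned.
- **Dose reductions (11.3, Appendix 7).** A patient who does not tolerate the starting dose steps down by 200 mg per dose, and "if that reduced dose is not tolerated, it will be reduced by a further 200mg". Withdrawal follows only if the second reduced dose is not tolerated. The example runs 600, 400, 200 mg t.d.s. The actual starting dose is left to Stage 1.
- **Analysis population (15.5).** Eligible patients who completed 14 days, with no dose condition.

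**The concern.** A patient reaches a reduced dose only because the dose above it was not tolerated. If that patient finishes 14 days, Section 14.4 read literally counts a success. Section 2.2.2.1 counts a success only if the dose is still one predicted to reach the target exposure. The same data can therefore meet the primary endpoint under one section and miss it under the other.

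This result feeds the decision on a definitive trial (9.1). The dose condition is also the part most able to fail: within a population defined by completing 14 days, completion itself is largely assured.

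The other safeguards do not close the gap. The rule on more than 20% of patients in 9.2.3 and 10 counts withdrawals for toxicity, and reduced patients have not withdrawn. The trough endpoint carries no required number of patients, and 14.4 names no summary of it.

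**Working it through.** **1. The plan's own threshold.** Exact (Clopper–Pearson) two-sided 80% interval for x of 18: lower limit is the 10% quantile of Beta(x, 19 − x), upper limit the 90% quantile of Beta(x + 1, 18 − x).

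| x/18 | 80% CI | Lower limit above 0.50? |
|---|---|---|
| 12 | 0.488 to 0.815 | no |
| 13 | 0.545 to 0.858 | yes |

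So 13 is the smallest passing count and the stated figure is reproduced. The threshold is sound. The issue is who enters the numerator.

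**2. The two numerators.**

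| Completer | 14.4 as written | 2.2.2.1 |
|---|---|---|
| At starting dose | counts | counts |
| Reduced, dose still predicted to reach target | counts | counts |
| Reduced, dose no longer predicted to reach target | counts | does not count |

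The sections differ only in the third row.

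**3. When the third row arises.** Three assumptions are needed:
- a 600 mg t.d.s. start (the example in 11.3);
- exposure proportional to dose, reading 1.5.4 ("The pharmacokinetics of micronized progesterone are reported as independent of dose") in that sense;
- the 50–150% band, which the protocol attaches to Stage 1 AUC and Stage 2 troughs, used to judge predicted exposure.

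Let S be the predicted exposure at the start, as a percentage of target.
- One step: 400/600 = 67%, leaving 0.67 × S. This is at least 50% of target when S ≥ 75.
- Two steps: 200/600 = 33%, leaving 0.33 × S. This is at least 50% only when S ≥ 150, the top of the band.

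With S = 100, one step gives about 67% (in band) and two steps about 33% (below it).

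**4. Illustration.** All 18 progesterone patients complete: 5 at the starting dose, 13 after two reductions, with that dose no longer predicted to reach target.
- 14.4: 5 + 13 = 18/18, met.
- 2.2.2.1: 5/18 = 28%, exact 80% CI 0.142 to 0.455, not met. (By symmetry with 13/18: 1 − 0.858 and 1 − 0.545.)
- Toxicity withdrawals: 0/18, so the 20% rule is silent.

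A milder split also reverses the result. With 13 completers, of whom 3 are on a non-qualifying dose, 14.4 gives 13/18 (met) and 2.2.2.1 gives 10/18 (80% CI 0.380 to 0.721, not met).

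**5. How often the verdicts could differ.** The protocol gives no completion or reduction rates, so these are assumptions. Let 85% complete at any dose and a share r of completers be on a non-qualifying dose. The chance of success is P(X ≥ 13) with X ~ Bin(18, p), where p = 0.85 under 14.4 and p = 0.85 × (1 − r) under 2.2.2.1.

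| r | p under 2.2.2.1 | 14.4 count | 2.2.2.1 count |
|---|---|---|---|
| 10% | 0.765 | 0.958 | 0.767 |
| 20% | 0.680 | 0.958 | 0.460 |
| 30% | 0.595 | 0.958 | 0.197 |

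With 90% completing, the figures are 0.994 against 0.890, 0.609 and 0.291.

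**The case against.** **The cross-reference.** The bullet in 14.4 is headed with a pointer to 2.2.2.1, so the dose condition could be read in. That is a fair reading, but 14.4 then writes out its own counting rule and twice describes tolerating treatment without naming a dose. An analyst following it would count every completer.

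**Reduced doses may still be on target.** A reader might infer that a twice-reduced patient is necessarily under-exposed. The documents do not support that. Section 1.5.3 expects 600–1800 mg/day in three divided doses to reach the target, and the three levels in Appendix 7 (3 × 200 = 600, 3 × 400 = 1200, 3 × 600 = 1800 mg/day) all lie in that range. The sentence in 1.5.4 comes from a product summary for 100–200 mg daily, while Section 2 says intermediate doses need further characterisation. This objection stands against any flat statement that reduced patients are off target. It does not remove the conflict, because Stage 1 exists to replace that extrapolation and 14.4 would ignore what it shows.

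**Other inferences to avoid.** Section 14.4 does not say that reduced patients tolerated the selected dose; it says only that they tolerated progesterone. Nor does 2.2.2.1 make every reduction a failure, since its condition is predicted exposure rather than the starting dose. An example built on many withdrawals would also mislead: 5 toxicity withdrawals are 5/18 = 28%, or 5/23 = 22% after replacement, and on an arm denominator either would trigger the 20% rule. Patients leaving for other reasons are replaced (9.2.2).

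**Troughs and the SAP.** Low troughs on reduced doses would be measured, which makes unnoticed under-exposure less likely, but they do not alter the 13/18 count. A SAP could classify reduced-dose completers. The protocol has, however, already stated the count and threshold in two conflicting ways, and a SAP can follow only one.

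**Conclusion.** The point holds as a contradiction between the endpoint definition and its counting rule, and it can reverse the Stage 2 go/no-go result. The wording gap needs no assumption.

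Its size is conditional. It depends on how many patients are reduced, for which the protocol gives no rate, and on which reduced doses Stage 1 still predicts to reach target. Under proportional exposure, a 600 mg t.d.s. start and a start predicted at about 100% of target, only two-step reductions fall outside 50–150%. With 85% completing and 20% of completers on a non-qualifying dose, the chance of passing is 0.96 on one wording and 0.46 on the other. The documents do not establish that reduced patients will be off target, only that 14.4 would count them if they were.

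**What to change.** Reconcile 14.4 with 2.2.2.1:

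- Count a progesterone patient toward 13/18 only if the dose being taken at Day 14 is still one predicted from Stage 1 to achieve the target exposure.
- Record which dose levels qualify when the Stage 2 dose is selected, and before unblinding.
- Tabulate completers at the starting, first-reduced and second-reduced dose, and report tolerability at any dose separately.

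This needs a wording change and one table from drug administration data already collected (14.3, Data Collection). The 13/18 threshold and its interval stay as they are. No dose or reduction rule is proposed. The downside is that 13/18 becomes harder to reach.
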